This study will examine whether greater WM capacity or practice is associated with increased or decreased anxiety during performance of a WM task during threat of shock. On the one hand, increase in WM capacity could be associated with more ability to allocate resources to anxious thoughts, therefore increasing anxiety. On the other hand, better WM reflects better ability to screen out intrusive stimuli and thoughts, thereby decreasing anxiety. As for task practice, we hypothesize that practice will make more resources available to allocate to anxious thoughts.

Subjects will be asked to remember verbal and nonverbal stimuli. These stimuli consist of words, pictures, letters or spatial locations in series of stimuli. Participants will be instructed to remember one, two, or three stimuli back from the current stimulus on the screen (n-back task). There will be 2 groups. One group will practice the N-back task

minimally (e.g., 5 min) and the other group will have more extensive training (e.g., 20 min).

Sub-study C: Effect of anxiety on sustained attention to response task (SART)

SART are sustained attention tasks during which a button-press response is made to frequent targets and responses are withheld to rare non targets. SART have been used extensively to study inattention, "off-task thinking", task-unrelated thoughts, and 'mind wandering" (Robertson, Manly et al. 1997). An advantage of this task is that it enables us to identify periods when the mind wanders. When the mind wanders, subjects make errors of commitment (they button-press to non-targets). We will use SART to attempt to identify periods of anxious thoughts.

Subjects will have to respond to frequent targets (e.g., digits 1, 2, 3...) and to withhold response to rare non targets (e.g., 3). We will examine the association between response speed and anxiety as assessed with startle. Mind wandering in SART is associated with faster RT. We will examine whether faster RT is associated with larger potentiated startle. We will also probe subjects' thoughts (on-task, off-task, anxious thoughts) after each startle stimulus to assess whether anxious thoughts predict startle potentiation.

Sub-study D: Effect of anxiety on Stroop task

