9. OUTCOME MEASURES

Primary outcome measures: The primary outcome measures will be the startle reflex, and performance on cognitive tasks.

Secondary outcome measures: These measures include psychophysiological measures other than startle (e.g., skin conductance), psychological questionnaires (Spielberger state and trait anxiety), and performance on standard cognitive tests (e.g., working memory capacity).

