10. STATISTICAL ANALYSIS

The accrual ceiling for this protocol is 1575 healthy controls. The overall current target N for the protocol is 148 healthy controls.

Sub-study A (previously Study 2a)36 subjectsSub-study C (previously Study 2c)34 subjectsSub-study E (previously Study 2e)48 subjectsSub-study F (previously Study 2f)30 subjects

Study 2a: Working memory and anxiety

Analysis of the data: Startle and performance data will be analyzed with ANOVAs with repeated measures using condition (threat, safe) x Load (low, high). Power analysis: Based on pilot and published works in our lab, we expect an small/moderate effect size for startle potentiation (Cohen's d=0.3). A priori calculations indicate that the testing of 30 participants at an alpha of 0.05 would provide power of 0.80 to detect a significant 2 (Condition) x 2 (Load) interaction on startle response. Assuming a 20% attrition rate, we will collect (about) 36 subjects.

Study 2c: Effect of anxiety on sustained attention to response task (SART)

Analysis of the data: The main analysis is to compare startle magnitude when subjects focus on the task and when their mind wander with ANOVAs with repeated measures using condition (threat, safe) x thought (on task, off task).

Power analysis: Based on pilot works in our lab, we expect an small/moderate effect size for startle potentiation (Cohen's d=0.4). A priori calculations indicate that the testing of 28 participants at an alpha of 0.05 would provide power of 0.80 to detect a significant 2 (Condition) x 2 (Load) interaction on startle response. Assuming a 20% attrition rate, we will collect (about) 34 subjects.

Study 2d: Effect of anxiety on Stroop task

Study is 2d is is closed for accrual. We are currently analyzing the data.

Study 2e: Pilot studies

These pilot experiments are designed to determine the parameter of stimulation of study that will be used in our neuroimaging, psychopharmacological, and clinical studies conducted in our other protocols (03-M-0093, 02-M-0321, 02-M-0263). We use tasks in 4 domains, 1) sensory processing, 2) conflict, 3) executive function, and 4) working memory. We will use 12 subjects per domain for a total of 48 subjects.

Study 2f: Pilot study of sural nerve stimulation

This pilot study investigates the location of the stimulating and recording electrodes and different types of stimulus delivery. We have requested 30 subjects.

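### Sub-study A asks whether working-memory capacity is associated with anxiety under threat, but no planned analysis estimates that association

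*Combined protocol and SAP*

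**What the plan says.** All references are to the combined protocol and SAP.

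- **Question (section 4(d), Sub-study A).** "This study will examine whether greater WM capacity or practice is associated with increased or decreased anxiety during performance of a WM task". For capacity the text offers two opposing possibilities. One is "increase in WM capacity could be associated with more ability to allocate resources to anxious thoughts, therefore increasing anxiety"; the other is that better WM screens out intrusive thoughts and so lowers anxiety. For practice it states one directional hypothesis.
- **Design (same place).** "There will be 2 groups. One group will practice the N-back task" minimally and the other more extensively. No WM capacity test, score or time of testing is named.
- **Measures (section 9).** The protocol-wide secondary list includes "performance on standard cognitive tests (e.g., working memory capacity"). Performance on the cognitive tasks is listed separately, as primary.
- **Analysis (section 10, Study 2a).** "Startle and performance data will be analyzed with ANOVAs with repeated measures using condition (threat, safe) x Load (low, high"). There is no covariate, correlation, regression or split by capacity, and no practice-group factor.
- **Power (same place).** "we expect an small/moderate effect size for startle potentiation (Cohen's d=0.3"), and "the testing of 30 participants at an alpha of 0.05 would provide power of 0.80" for the Condition x Load interaction on startle. Enrolment is set at about 36 to allow for 20% attrition.

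**The concern.** The question is about differences between people: do those with more capacity show more or less startle potentiation under threat? The model is about differences between task conditions within a person. A significant or a null Condition x Load result would therefore not favour either of the two capacity predictions.

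The predictions point in opposite directions, so either sign of an association found later could be presented as expected. If the capacity score, the contrast and the model are all chosen after the data are seen, the result will be hard to interpret. A reader could also take the 80% power statement to cover the capacity question, which it does not.

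**Working it through.** **1. What the planned model estimates.** For subject i, take startle under threat (T) and safe (S) at low and high load.

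- Potentiation averaged over load: P_i = ½[(T_low − S_low) + (T_high − S_high)].
- Change in potentiation with load: D_i = (T_high − S_high) − (T_low − S_low).

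In the planned ANOVA the Condition effect tests whether mean P is zero, and Condition x Load tests whether mean D is zero. The capacity question concerns b in

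P_i = a + b(C_i − mean C) + g·Group_i + error,

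where C_i is capacity. No term in the planned model corresponds to b. N-back performance enters section 10 only as an outcome, so it does not supply b either.

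**2. The plan's own figure.** Inputs from section 10: d = 0.3, N = 30, alpha 0.05, power 0.80. Sidedness, the standardiser of d and the within-subject correlation are not stated.

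- The 2 x 2 interaction is a single-degree-of-freedom contrast. If d is the standardised mean of that contrast, the noncentrality is 0.3 × √30 = 1.64 on 29 df. Power is then 0.36 two-sided (0.48 one-sided), and 80% power needs N = 90 (71 one-sided).
- If instead f = d/2 = 0.15 with four measurements and an assumed within-subject correlation of 0.7, lambda = 0.15² × 30 × 4 / (1 − 0.7) = 9.0. Power is then 0.83, and 80% power is reached at N = 29.

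So N = 30 does not follow from the stated inputs alone, but an unstated correlation can produce it. The present point does not depend on which reading was meant, because the figure concerns Condition x Load either way.

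**3. What 30 subjects give for capacity.** Test of r between capacity and P, two-sided 0.05, by Fisher's z: smallest detectable |r| = tanh[(1.960 + 0.842)/√(n − 3)].

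- n = 30: tanh(2.802/√27) = tanh(0.539) = 0.49.
- n = 36 (no attrition): tanh(2.802/√33) = 0.45.
- n = 30, also adjusting for practice group (one further df): tanh(2.802/√26) = 0.50.

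The documents give no expected r, so the range below is assumed. Power = Φ(atanh(r)·√27 − 1.96), plus a negligible opposite tail; N for 80% = (2.802/atanh r)² + 3.

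| Assumed r | Power at n = 30 | N for 80% power |
|---|---|---|
| 0.2 | 0.18 | 194 |
| 0.3 | 0.36 | 85 |
| 0.4 | 0.60 | 47 |
| 0.5 | 0.81 | 30 |

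Precision: an observed r of 0.3 at n = 30 has a 95% interval of tanh(0.310 ± 1.96/√27), that is, −0.07 to 0.60.

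**The case against.** **Capacity is not the main aim.** The question joins capacity and practice. Practice carries the only explicit hypothesis and the only design feature, the two training groups. Capacity is secondary in section 9, where it is an example in a list, and section 10 gives no model for any secondary measure. This stands as a limit on emphasis: that capacity is named first does not make it the leading question. It does not remove the gap, because section 4(d) poses the question in its own right and nothing labels it exploratory.

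**Load could stand in for capacity.** It cannot. Load is a demand of the task, set equally for every subject; section 4(d) treats capacity as a property of the person.

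**A formal test at this size is weak.** This stands, and it argues for a secondary or exploratory label with an interval estimate. It is not a reason to leave the analysis unspecified.

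Three stronger readings are tempting, and the documents do not support them.

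- *That the planned ANOVA would come out the same whatever the capacity relation.* Capacity-related spread between subjects can enter the error term and change F and p. The supportable statement is that the ANOVA does not estimate the slope.
- *That adding capacity would raise power for Condition x Load.* No correlation between capacity and that contrast is given. The 80% starting point does not follow from d = 0.3 if d is the standardised contrast (step 2). The capacity question also concerns a different contrast, capacity x Condition.
- *That the change is wording only.* No capacity test, score or timing is tied to Sub-study A, so the procedures may need an addition.

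**Conclusion.** The point holds as a gap in the analysis plan. Sub-study A poses a capacity question and section 10 specifies no analysis that estimates the association. This follows from the text and needs no numerical assumption. It does not invalidate the Condition x Load test.

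The size of what the sub-study could say about capacity rests on 30 analysed subjects, a two-sided 5% test and roughly bivariate-normal scores. On those terms, 80% power requires |r| of about 0.49, or about 0.50 after adjusting for practice group; at r = 0.3 power is about 36%. A null finding would therefore be weak evidence of no association. The amendment is worth making, but it ranks below a flaw in the primary test.

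**What to change.** In section 10, Study 2a:

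- Add mean-centred WM capacity as a continuous covariate, with its Condition and Condition x Load interactions, in a model that also carries the practice-group factor. Adding capacity alone would pool minimally and extensively trained subjects.
- Name capacity x Condition on startle as the analysis of the capacity question, and report the slope with its 95% confidence interval.
- State that the 80% power applies to Condition x Load only. Give the detectable |r| of about 0.49 at n = 30 (about 36% power at r = 0.3), and label the capacity analysis secondary or exploratory.

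In sections 4(d) and 9:

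- Name which standard cognitive test supplies the capacity score and how it is scored. Take it before the practice manipulation, so that training cannot alter it.
- Describe capacity as a predictor for Sub-study A.

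Cost: no extra subjects. Each within-subject contrast loses one error degree of freedom for capacity and one for group (29 to 27 at n = 30), and more if further interactions are added. A capacity test must be specified and, if it is not already given, added to the session. The power statement for this question will be unfavourable.

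### The 80% power stated for Sub-studies A and C does not follow from the stated effect sizes and sample sizes, and C's power sentence names an interaction that C does not test

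*Combined protocol and SAP*

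**What the plan says.** The power statements are in section 10, Statistical Analysis, under Study 2a (now Sub-study A) and Study 2c (now Sub-study C).

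- **Sub-study A.** Startle and performance are analysed by "ANOVAs with repeated measures using condition (threat, safe) x Load (low, high". On effect size: "we expect an small/moderate effect size for startle potentiation (Cohen's d=0.3". On power: "testing of 30 participants at an alpha of 0.05 would provide power of 0.80 to detect a significant 2 (Condition) x 2 (Load) interaction". Enrolment is set at about 36 to allow for 20% attrition.
- **Sub-study C.** The main analysis of startle is by "ANOVAs with repeated measures using condition (threat, safe) x thought (on task, off task". The stated input is an "effect size for startle potentiation (Cohen's d=0.4", and the power claim is "testing of 28 participants at an alpha of 0.05 would provide power of 0.80 to detect a significant 2 (Condition) x 2 (Load) interaction". Enrolment is set at about 34.

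Section 4 explains where C's thought factor comes from: subjects are probed for their thoughts ("on-task, off-task, anxious thoughts) after each startle stimulus"). It describes no load manipulation in C.

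Section 10 gives no definition of d (which standard deviation it is scaled by), no correlation between repeated measures, no sidedness and no formula or software.

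**The concern.** Three things do not fit together.

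1. In a fully within-subject 2 x 2 design the interaction is a one-degree-of-freedom contrast, equivalent to a paired t test on each subject's difference of differences. For such a test, 30 subjects at d = 0.3 is far from 80% power unless d is rescaled by a high correlation, and none is stated.
2. At fixed power, n varies roughly as 1/d². Going from d = 0.4 to d = 0.3 should raise n by about 78%, but the plan moves only from 28 to 30.
3. The effect size is for threat minus safe, while power is claimed for whether that difference changes with load or thought. The first does not determine the second. In C, the factor named in the power sentence is not in the design.

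These two sentences alone support 36 + 34 = 70 of the 148 target subjects (47%). Sub-studies E and F are pilots without a power statement. A reader cannot tell what size of interaction A or C could detect, and for C no power is stated for the analysis that will be run.

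**Working it through.** **Inputs from section 10.** A: d = 0.3, n = 30. C: d = 0.4, n = 28. Both: alpha 0.05, power 0.80.

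**Assumptions.** Two-sided test (the usual F test for an interaction). The correlation r between repeated measures is not given, so it is varied.

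**Formula.** For the 1-df interaction, power = P(F′ > F_crit), where F′ is noncentral F with 1 and n − 1 degrees of freedom and noncentrality λ = n·d_z². Here d_z is the mean interaction contrast divided by its standard deviation across subjects.

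**Step 1: try to reproduce 0.80 with d taken as d_z.**

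| | λ | Power | n for 80% |
|---|---|---|---|
| A | 30 × 0.3² = 2.70 | 0.355 | 90 |
| C | 28 × 0.4² = 4.48 | 0.532 | 52 |

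One-sided testing gives 0.484 and 0.662. The stated figure is not reproduced.

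**Step 2: what 0.80 requires.** At n = 30 the d_z needed is 0.529; at n = 28 it is 0.549. So d must be multiplied by 0.529/0.3 = 1.764 in A and by 0.549/0.4 = 1.373 in C.

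**Step 3: can a correlation supply that multiplier?** Three conventions for d:

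- (i) ANOVA effect size f = d/2, four cells, 1 df: λ = 4nf²/(1 − r), so d_z = d/√(1 − r).
- (ii) Paired difference in raw-SD units: d_z = d/√(2(1 − r)).
- (iii) Difference of differences in cell-SD units: d_z = d/√(4(1 − r)).

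| Convention | r needed, A | r needed, C | Power A, r 0.3 to 0.7 | Power C, r 0.3 to 0.7 |
|---|---|---|---|---|
| (i) | 0.68 | 0.47 | 0.48 to 0.83 | 0.68 to 0.96 |
| (ii) | 0.84 | 0.73 | 0.27 to 0.54 | 0.41 to 0.75 |
| (iii) | 0.92 | 0.87 | 0.16 to 0.31 | 0.23 to 0.46 |

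Each line can be matched alone, but the correlations differ within every convention. An omnibus version (f = d/2, four measurements, 3 and 3(n − 1) df) needs 0.763 and 0.608, again unequal. Entering d directly as f (two measurements, r = 0.5) overshoots: power 0.888 and 0.983, with 24 and 15 subjects needed. A wider search over definitions of d and f, two or four measurements, one or two groups, and r from 0 to 0.95 found no shared setting that put both powers within two points of 0.80.

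**Step 4: cross-check that does not depend on the convention.** In conventions (i) to (iii), d_z is d times a factor set by r, so a shared convention and r mean a shared factor.

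- C's factor applied to A: d_z = 1.373 × 0.3 = 0.412; power at n = 30 is 0.59, and 49 subjects are needed.
- A's factor applied to C: d_z = 1.764 × 0.4 = 0.706; power at n = 28 is 0.95, and 18 subjects are needed.

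The approximate scaling agrees: 28 × (0.4/0.3)² = 49.8 and 30 × (0.3/0.4)² = 16.9, against a planned ratio of 30/28 = 1.07 where (0.4/0.3)² = 1.78.

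**Step 5: compare C's analysis with C's power sentence.** The analysis sentence crosses condition with thought (on or off task). The power sentence crosses condition with load. Thought is taken from probe responses, so how many startle trials fall in each cell depends on the subject. In A, load is set by the design.

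**The case against.** The strongest reply is that this is missing detail rather than an error. A and C are different tasks: load is imposed in A, thought is self-reported in C. Their effect sizes also come from different sources, pilot and published work for A and pilot work only for C. Nothing requires them to share a correlation, and with separate correlations each n is attainable. If 0.80 is read as a floor, one correlation even satisfies both sentences, with A at 0.80 and C at 0.95. A mixed reading also comes close: section 4 lists one-, two- and three-back levels, and six cells for A with four for C (f = d/2, r = 0.5, 1 df) gives 0.785 and 0.823. Finally, Load in C's sentence may be a label carried over from A. Both tests have 1 df, so correcting the word would leave the arithmetic unchanged.

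Part of this stands. Neither n is shown to be impossible, and no actual power shortfall is proved: under convention (i), 0.80 lies inside the range for both sub-studies. The 0.36 and 0.53 hold only if d is the standardised interaction.

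The rest does not remove the problem. The sentences read as point values, not floors. They specify a 2 x 2 design with load at two levels, which excludes the six-cell reading. If the correlations differ, the plan has to state them and say why. Relabelling C's factor would still leave an effect size for potentiation standing in for an interaction.

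**Conclusion.** The concern holds. The 80% power in each sentence does not follow from the inputs given, and no common convention and correlation tested yields both n = 30 at d = 0.3 and n = 28 at d = 0.4. With d as the standardised interaction and a two-sided 0.05 test, power is about 0.36 (A) and 0.53 (C). Under the three correlation-based conventions with r assumed between 0.3 and 0.7, it ranges from 0.16 to 0.83 (A) and from 0.23 to 0.96 (C). That spread is the practical consequence of leaving d and r undefined. C's power sentence is wrong as written whatever the arithmetic, because it names a factor C does not have. Confidence is high on the omissions, the mismatch between the two lines and C's wrong factor. The true power remains unknown. This should be fixed.

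**What to change.** Replace both power sentences in section 10. For each sub-study:

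1. Name the tested contrast: Condition x Load in A, Condition x Thought in C.
2. Give the assumed standardised size of that interaction (not of startle potentiation) and say which standard deviation it is scaled by.
3. State the within-subject correlation. If it differs between A and C, say so and why.
4. Report the power the planned n delivers under those assumptions (about 0.36 for A and 0.53 for C if the present d values are meant as standardised interactions). Alternatively, state the smallest interaction detectable at 80% power: d_z about 0.53 with 30 completers and 0.55 with 28.

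The cost is protocol wording only, with no added enrolment and no change to the analysis. The stated power may become less favourable, depending on the contrast and correlation declared.

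### Sub-study C: the main ANOVA sorts startles by the subject's own thought reports, so 28 subjects with all four cells filled are not secured, and empty cells are neither allowed for nor handled

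*Combined protocol and SAP*

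**What the plan says.** Section 10 (Study 2c) makes the main analysis a comparison of startle magnitude between on-task and mind-wandering moments, "with ANOVAs with repeated measures using condition (threat, safe) x thought (on task, off task"). Both factors are within subject.

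Section 4 (Sub-study C) explains how the Thought factor arises: "We will also probe subjects' thoughts (on-task, off-task, anxious thoughts) after each startle stimulus". The subject has three possible answers; the ANOVA has two levels. The plan does not say where anxious thoughts go.

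On sample size, section 10 states "we expect an small/moderate effect size for startle potentiation (Cohen's d=0.4") and that "the testing of 28 participants at an alpha of 0.05 would provide power of 0.80". The effect named is to "detect a significant 2 (Condition) x 2 (Load) interaction on startle response", although sub-study C's ANOVA has no Load factor. Then: "Assuming a 20% attrition rate, we will collect (about) 34 subjects".

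The documents give no number of startle probes per condition, no expected off-task rate, no minimum number of startles per cell, and no rule for an empty cell.

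**The concern.** The experimenter fixes how many startles fall under threat and safety. The subject's answers fix how many of those are on task or off task. Someone who never reports being off task (or never on task) in one condition has no mean for that cell, and a within-subject 2 x 2 ANOVA on cell means cannot use that person.

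Three things are at stake:

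- **Numbers.** The analysed sample can fall below 28 even when every subject finishes the session.
- **Selection.** Who is dropped depends on mind-wandering frequency, which is what the sub-study is about. Those kept report both states under both conditions.
- **Precision.** Subjects who stay in contribute cells of very unequal size, all weighted alike.

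**Working it through.** **1. The plan's own figure.** The interaction in a 2 x 2 within-subject ANOVA is a one-sample t test on each subject's difference of differences. Reading d = 0.4 as the standardised size of that contrast, the noncentral t with n = 28 and two-sided alpha 0.05 (sidedness is not stated) gives 53% power; 80% needs 52 subjects. Some undocumented settings do come near 28, for example f = 0.2 with four measurements correlated at 0.61. So 28 is not reproduced on the direct reading, but it is not shown to be impossible. That, and the naming of Load, are separate points. Below I take 28 as giving 80%, which implies a contrast of d = 0.549.

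**2. Reserve in the enrolment figure.** 28 x 1.2 = 33.6, rounded to 34, appears to be the source. Removing 20% from 34 leaves 34 x 0.8 = 27.2. Dividing instead gives 28/0.8 = 35. The difference is small, but nothing is left over for empty cells.

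**3. How many subjects have an empty cell.** The inputs are assumptions: k probes per condition, and an off-task probability p that varies between subjects as a beta distribution and is the same under threat and safety. For one subject:

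P(complete | p) = [1 - p^k - (1 - p)^k]^2

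and this is averaged over p. For a hand check, if every subject had p = 0.25 and k = 12, then 0.75^12 = 0.032 and 1 - 0.968^2 gives about 6% incomplete. Variation between subjects (SD 15%) raises this to 21%. Share of subjects with at least one empty cell:

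| Probes per condition | Off-task 35% (SD 18%) | 25% (SD 15%) | 15% (SD 10%) |
|---|---|---|---|
| 8 | 20% | 33% | 54% |
| 12 | 11% | 21% | 39% |
| 16 | 7% | 15% | 30% |
| 24 | 4% | 8.5% | 19% |

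**4. Consequence for numbers and power.** Let c be the share of retained subjects who are complete. Complete subjects are 27.2c (rounded down), and enrolment for 28 complete subjects is 28/(0.8c):

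| c | Complete from 34 | Power if d = 0.549 | Enrolment for 28 |
|---|---|---|---|
| 1.0 | 27 | 78% | 35 |
| 0.9 | 24 | 73% | 39 |
| 0.8 | 21 | 67% | 44 |
| 0.7 | 19 | 62% | 50 |
| 0.5 | 13 | 45% | 70 |

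These powers count lost subjects only, not the extra noise from thin cells.

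**5. Unequal cells.** Take 9 probes per condition and residual variance s². A subject with 1 off-task and 8 on-task reports in each condition has contrast variance 2 x (1 + 1/8)s² = 2.25s². One with 4 and 5 has 2 x (1/4 + 1/5)s² = 0.90s². The ANOVA treats the two alike.

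**6. ANOVA against a trial-level model.** Simulation, all inputs assumed: 28 subjects, 9 probes per condition, off-task mean 25% (SD 15%), residual SD 25, intercept SD 30, Condition-slope SD 10. On average 20 of 28 subjects are complete.

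- No between-subject variation in the Thought or interaction effect: power is 40% (ANOVA) against 58% (trial-level) for an interaction of 12 units, and 73% against 90% for 18 units, with variances treated as known. A REML fit that estimates them gives 42% against 61% and 78% against 91%; its false-positive rate was 7% in 200 runs, within simulation error of 5%.
- With such variation (Thought SD 10; interaction SD 10, 20 or 30), a model with only a random intercept and Condition slope has false-positive rates of about 7%, 12% and 21%. The ANOVA stays at 4% to 6%.
- With random slopes for Thought and the interaction added (variances treated as known), the rate is 4% to 5%. Power for 18 units is 68% against 57% for the ANOVA at interaction SD 20, and 56% against 49% at SD 30.

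**The case against.** A reader might infer that the planned 28 cannot be analysed. The documents do not support that. The loss turns on two quantities they do not give. With 24 probes per condition and a 40% off-task rate, 27 to 28 of 28 subjects would be complete.

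The 20% may also hold some reserve. Testing is a single session and loss to follow-up is marked as not applicable, so part of the allowance could be meant for unusable data. If all 34 gave usable startle, the 12-probe scenarios would leave 34 x 0.89 = 30, 34 x 0.79 = 27 and 34 x 0.61 = 21 complete subjects. This stands as a possibility, but the plan does not define attrition that way, and even then one of the three scenarios falls well short of 28.

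The calculation uses two thought categories and the same rate under threat and safety. Counting anxious thoughts as off task would raise the off-task share and, at these rates, fill cells; leaving them out would empty more. The direction of the error is unknown until the plan says which applies.

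Nor is the ANOVA invalid: it holds its error rate among complete subjects. A trial-level model without the Thought and interaction slopes could be worse than what it replaces.

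**Conclusion.** The mechanism follows directly from sections 4 and 10: Thought is self-sorted, a cell-mean ANOVA loses subjects with an empty cell, and the plan neither estimates nor handles that loss. 28 complete subjects are therefore not secured, since 34 less 20% is already 27.2. How many would be lost is not known. It is about 4% to 54% of subjects under 8 to 24 probes per condition and 15% to 35% mean off-task share, with the between-subject SDs shown above. The loss is selective on mind-wandering frequency, so the result would describe subjects who report both states under both conditions rather than all those tested.

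A reader might also infer that a mixed model lets every subject inform the interaction. It does not: someone who reports a single thought state carries almost no within-subject information on it. The model recovers precision and partly filled subjects, and cures the selection only in part.

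**What to change.** In section 10, Study 2c, make the main analysis a linear mixed model on single-startle magnitudes with:

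- fixed Condition, Thought and Condition x Thought;
- by-subject random intercept and random slopes for Condition, Thought and their interaction, simplified only by a rule stated in advance if the model does not converge;
- small-sample degrees of freedom, for example Kenward-Roger;
- the within-subject Thought effect separated from each subject's mean off-task rate.

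State whether anxious thoughts count as off task or form a third level. State the probes per condition and the expected off-task rate, so that the likely number of complete subjects can be worked out. Keep the cell-mean ANOVA as a sensitivity analysis and report how many subjects have all four cells filled.

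The cost is SAP wording: section 4 already ties a thought report to each startle, so no new data are needed. The downsides are a model that is harder to explain and may not converge with about 28 subjects.
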